4.6. IDENTIFICATION OF ALL SOURCE DATA NOT INCLUDED IN THE MEDICAL RECORD

Source data not included in the medical record corresponds to data not routinely collected in the medical and paramedical records.

In this study: The assessment by the childcare assistant of the grade of pressure ulcer reported on a data collection sheet will be considered as the source data.

4.7. RULES FOR DISCONTINUING A PERSON'S PARTICIPATION

4.7.1. Criteria for premature termination of a person's participation in the research

Subjects may withdraw their consent and request to leave the study at any time and for any reason. In the event of premature withdrawal, the investigator must document the reasons as fully as possible.

The investigator may temporarily or permanently discontinue a subject's participation in the study for any reason that is in the best interests of the subject, particularly in the event of serious adverse events.

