In a 2013 article in the Paediatric Journal (10), various medical devices responsible for pressure ulcers are listed, such as intubation tubes, drains, orthopaedic splints, nasogastric tubes, oxygenation systems and intravenous catheters. Clinicians have identified that MDs positioned in contact with the skin can lead to the development of pressure ulcers. Although the aetiology of

pressure ulcers related to immobility and those related to MDs is different, the mechanism of wound formation is similar.

Few articles specifically discuss pressure ulcers associated with VVP.

These pressure ulcers associated with medical devices are not without consequences for children. In addition to skin damage, there is also psychological trauma related to the care and pain caused by the bedsores, which can make future treatment difficult (10).

An international classification system for pressure ulcer stages was established in 1998 by the National Pressure Ulcer Advisory Panel (8). This scale, which was initially validated on an adult population, is perfectly applicable to the classification of pressure ulcers in children.

Paediatric nurses use it systematically when removing catheters to assess the stage of the pressure ulcer. The pressure ulcers observed in our department and linked to the junction between the catheter and the extension tube are mainly stage I pressure ulcers.

In order to limit the occurrence of these pressure ulcers, specific recommendations are described by the NPUAP (8). These primarily concern the selection and assembly of the medical device. The device must be examined and selected within the institution so that the pressure and shear forces cause as little damage as possible. It must be used correctly in accordance with the manufacturer's specifications.

In addition, the skin and medical device must be inspected at least twice a day.

It is also recommended to keep the skin under the medical devices clean and dry and to use prophylactic dressings to reduce pressure at the skin-device interface.

As soon as medically possible, all medical devices that are a potential source of pressure sores should be removed.

In the Paediatrics Department at CHD Vendée, we try to follow these recommendations as closely as possible.

The equipment is selected by the pharmacy and the medical devices team.

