4.7.2. Procedures for premature termination of a person's participation in research

In the event of withdrawal of consent, data already collected may be analysed unless the patient objects.

Their medical care will be identical to the usual care provided to this type of patient in the department.

The information to be collected is:

- Date of end-of-study visit
- Reason for early withdrawal

For information on how data from individuals who withdrew prematurely from the study will be used, please refer to the statistics section.

4.7.3. Criteria for discontinuing part or all of the research (excluding biostatistical considerations)

The CHD de Vendée reserves the right to interrupt the study at any time if it appears that the inclusion objectives are not being met.

Part or all of the study may be terminated permanently or temporarily by decision of the ANSM, the CPP or the study sponsor.

Written confirmation will be sent to the study coordinator (specifying the reasons for premature termination).

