5.2.7. Selection of individuals to be included in the analyses

The primary analysis will be performed on the intention-to-treat (ITT) population, i.e. all randomised patients.

A complementary analysis will be performed on the Per Protocol (PP) population, including randomised patients for whom no major deviations from the protocol have been identified.

A data review meeting will be organised to review and define whether each deviation is a major criterion or not.

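### After investigator discontinuation, section 4.7.2 does not ask for the skin grade at catheter removal, so a child may be counted as ulcer-free without having been assessed

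*Combined protocol and SAP*

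**What the plan says.** Section 4.7.1 describes two routes out of the study. The family may withdraw consent at any time. Separately, "The investigator may temporarily or permanently discontinue a subject's participation in the study for any reason", provided it serves the child's best interests; the one example given is serious adverse events.

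Section 4.7.2 gives a single procedure for premature termination. It introduces its list with "The information to be collected is" and names two items: the date of an end-of-study visit, and "Reason for early withdrawal". The NPUAP grade, the time of catheter removal and infection status are not on the list. Use of earlier data is settled for one route only: "In the event of withdrawal of consent, data already collected may be analysed unless the patient objects". For everything else the section points onward: "For information on how data from individuals who withdrew prematurely from the study will be used, please refer to the statistics section".

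The statistics section has no rule written for these children. Section 5.2.7 states: "The primary analysis will be performed on the intention-to-treat (ITT) population, i.e. all randomised patients". Section 5.2.5 scores a missing primary outcome as absence of a pressure ulcer, in either arm.

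The primary endpoint is assessed once, at catheter removal (section 4.1, its schedule table, and section 5.2.1). The assessor is a childcare assistant who has not cared for the child, and such staff are available round the clock (section 4.5). Section 4.7.2 says that usual departmental care continues after early termination. Section 1.1 says of the NPUAP scale in routine practice: "Paediatric nurses use it systematically when removing catheters to assess the stage of the pressure ulcer".

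**The concern.** Ending a child's participation and refusing further data are different events, and only the second removes the right to look at the skin on removal day. Section 4.7.2 treats them alike. Because the endpoint has a single time point, data already collected before removal cannot include it. The planned intention-to-treat analysis then has no observation for a child whose outcome could have been obtained with no extra visit.

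The two statistical rules make this more than missing detail. The child stays in the denominator and is entered as a non-event. If losses are similar in both arms, the difference shrinks. If they differ by arm, the comparison is biased. The trial is open (section 4.2) and the investigator is a nurse (section 7.6.1), so the decision to discontinue can be made with the allocation known.

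This point concerns what is collected. A different missing-data rule would change the damage but would not recover an assessment that nobody was asked to make.

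**Working it through.** **1. Following one child through the text.** A child is randomised and the catheter is placed. The investigator discontinues participation before removal, and consent is not withdrawn.

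- Section 4.7.2 asks for a date and a reason. It does not ask for a grade.
- The schedule table has three columns: inclusion, every day, and the day the catheter is removed. No end-of-study visit appears. The term may mean removal day, but no section says so.
- If no grade is taken, section 5.2.5 enters no ulcer and section 5.2.7 keeps the child in the analysis.

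**2. The plan's own sample size.** Section 5.2.2 gives 346 patients for a 15-point difference, 80% power and 5% alpha, with 360 randomised 1:1 (180 per arm). The control rate and sidedness are not stated. I assume a two-sided test and rates near 50%, using the pooled formula

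n per arm = [1.96·√(2p̄q̄) + 0.8416·√(p₁q₁ + p₂q₂)]² / d²

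At 55% vs 40%: p̄ = 0.475, 2p̄q̄ = 0.49875, p₁q₁ + p₂q₂ = 0.4875, so n = (1.3842 + 0.5876)² / 0.0225 = 172.8. That rounds up to 173 per arm, or 346. The figure reproduces. (57.5% vs 42.5% gives 348; 50% vs 35% gives 340.)

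**3. One missed ulcer.**

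- Scored as no ulcer: 1/180 = 0.56 points off that arm's rate.
- Excluded instead, assuming 90 ulcers in 180: 90/180 = 50.00% becomes 89/179 = 49.72%, a shift of 0.28 points. About half of the 0.56 therefore comes from the scoring rule and the rest from the absent observation.

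**4. Equal loss in both arms (assumed fraction m).** If a fraction m of children is lost regardless of outcome and scored as no ulcer, both rates are multiplied by (1 − m), and so is the difference. Power at n = 180 per arm is Φ{[d√n − 1.96√(2p̄q̄)] / √(p₁q₁ + p₂q₂)}.

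| m (assumed) | Difference | Power, 57.5% vs 42.5% | Power, 50% vs 35% |
|---|---|---|---|
| 0 | 15.0 points | 81.5% | 82.4% |
| 2% | 14.7 points | 79.9% | 81.0% |
| 5% | 14.25 points | 77.5% | 78.9% |
| 10% | 13.5 points | 73.2% | 75.2% |

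If lost children were excluded rather than scored, power at 57.5% vs 42.5% would be 79.5% at m = 5% and 77.3% at m = 10%.

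**5. Loss in one arm only (a bounding case, not a forecast).** Take no true effect, a 50% rate, and losses in the compress arm alone. At 5% lost, the apparent benefit is 0.50 × 0.05 = 2.5 points, and the chance of a significant result favouring the compress is about 7%, against a nominal 2.5%. At 10% lost, the figures are 5 points and about 16%. No discontinuation rate in the documents supports either fraction.

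**The case against.** Several parts of the opposing case stand.

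- Section 4.7.2 does not say that only two items are collected, or that planned assessments stop. Section 5.1.1 requires the eCRF to hold everything the analysis needs. Appendix 3 (data collected) is listed by title, but its content is not in the available text and might cover this.
- Participation runs until catheter removal (section 4.1), so the end-of-study visit may be removal day, when the grade is taken anyway. The text is ambiguous; it does not order the outcome to be dropped.
- A reader might infer that losses will gather in the compress arm because local problems under the dressing lead to discontinuation. The documents do not support that. Redness or discharge at the puncture site is the stated exception to keeping the line until treatment ends (section 4.1), and removal is the moment of assessment. A soiled compress leads to a dressing change (section 4.5). The only example of a reason for discontinuation is serious adverse events.
- A reader might also infer from section 1.1 that routine grading already supplies the primary outcome. It does not. Nurses give that grade unblinded. The endpoint is the blinded assistant's grade, recorded on a study sheet that section 4.6 treats as source data outside the medical record.

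What remains is that no available passage asks for the blinded grade after discontinuation, and that the section to which 4.7.2 refers supplies only the non-event rule.

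**Conclusion.** The point holds as a gap in the collection rule. Section 4.7.2 merges investigator discontinuation with withdrawal of consent and does not ask for the removal-day grade. A child discontinued earlier can therefore be analysed as ulcer-free although an assessment was obtainable.

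The size is probably small, since follow-up ends at catheter removal, but it cannot be fixed because no discontinuation rate is given. The firm figure is 0.56 points per missed ulcer, which depends on 180 per arm and on the rule in section 5.2.5. The power and one-arm figures rest on assumed ulcer rates and loss fractions. A reader might take the one-arm case as evidence of a bias of several points; the documents do not support that, because they give neither a rate nor a reason to expect losses in one arm. The sample size, alpha and power statements need no change.

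**What to change.** In section 4.7.2:

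- Separate investigator discontinuation from withdrawal of consent.
- After investigator discontinuation without withdrawal of consent or objection, state that the following are still collected at catheter removal: the blinded childcare-assistant NPUAP grade, the date and time of removal, infection status, and the reason for discontinuation. Clinical decisions stay with the investigator.
- After withdrawal of consent, collect nothing further unless the family agrees.
- If a routine nurse grade is ever used instead, flag it as unblinded and do not merge it into the blinded primary endpoint.
- Replace the end-of-study visit with catheter removal, or define it, and check that Appendix 3 agrees.

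The cost is protocol wording and a line on the existing collection sheet. No visit or staff are added, because the catheter is removed in the department anyway. The downside is that the information sheet may need one sentence on continued collection.

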4.7.2. Procedures for premature termination of a person's participation in research

In the event of withdrawal of consent, data already collected may be analysed unless the patient objects.

Their medical care will be identical to the usual care provided to this type of patient in the department.

The information to be collected is:

- Date of end-of-study visit
- Reason for early withdrawal

For information on how data from individuals who withdrew prematurely from the study will be used, please refer to the statistics section.

4.7.3. Criteria for discontinuing part or all of the research (excluding biostatistical considerations)

The CHD de Vendée reserves the right to interrupt the study at any time if it appears that the inclusion objectives are not being met.

Part or all of the study may be terminated permanently or temporarily by decision of the ANSM, the CPP or the study sponsor.

Written confirmation will be sent to the study coordinator (specifying the reasons for premature termination).

5. DATA MANAGEMENT AND STATISTICS

5.1. *COLLECTION AND PROCESSING OF STUDY DATA*

5.1.1. *Data collection*

An electronic case report form (eCRF) will be created for each patient. All information required by the protocol must be provided in the eCRF. It must include the data necessary to confirm compliance with the protocol and all data necessary for statistical analysis; it must allow for the detection of major deviations from the protocol.

The persons responsible for completing the eCRFs (investigator, ARC, etc.) must be defined and identified in the table of delegated responsibilities (kept in the investigator's binder).

5.1.2. *Data coding*

By signing this protocol, the principal investigator and all co-investigators undertake to keep the identities of the patients who participated in the study confidential.

The transmission of an individual's data for research purposes will therefore only be possible subject to the application of a coding system; the presentation of research results must exclude any direct or indirect identification.

Patients will be identified according to the order of patient inclusion by a number automatically assigned by the Clinsight software (eCRF) and then supplemented by the patients' initials.

This code will be the only information appearing on the eCRF that will allow the eCRF to be linked to the patient at a later date.

The research manager is also required to code patient data on all documents in their possession that may be attached to the CRF.

A correspondence table will be set up at the centre. This table will be kept in a secure location by the centre's principal investigator and will contain the patient code and their personal data, so

that the patient file can be traced in the event of missing or incorrect data. No clinical data will be collected in these correspondence tables.

5.1.3. Data processing

Clinical data will be collected using a database and data entry forms modelled on the observation log, in accordance with the protocol and current regulations.

5.2. STATISTICS

Responsible for statistical analysis:

[name]
Vendée Departmental Hospital Centre
Clinical Research Unit
[contact]

Software

The analyses will be performed using R software version 3.5.1

5.2.1. Description of planned statistical methods, including the schedule for planned interim analyses

All variables will be described globally and by group. The description will include the numbers and percentages of modalities for qualitative variables and the minimum, maximum, mean, standard deviation and median for quantitative variables.

Primary endpoint

The primary endpoint is defined as the presence of a pressure ulcer at the junction of the catheter with the extension tube or peripheral venous line tubing. The assessment will be performed upon catheter removal and blinded by a nursing assistant from the department.

The percentage of patients will be presented with a 95% confidence interval in the two groups and will be compared using a Chi-square test.

In a second step, the two groups will be compared using logistic regression to take into account the duration of catheter retention.

Secondary criteria

The severity of pressure ulcers will be described between the two groups. At each stage of the NPUAP scale, the number and percentage of patients will be presented. A Mann-Whitney test will be applied to compare the two groups.

The average duration of catheter retention will be described for the two groups with a 95% confidence interval. It will be compared using a Student's t-test.

The number of patients with nosocomial infection will be described in the two groups. No statistical test will be performed.

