is more prominent and is pressed against the skin by the occlusive dressing used to maintain the PIV. Regardless of the type of equipment used and the brand, this junction is always present. These pressure sores, which can cause pain and scarring on a child's skin, are difficult for a nurse to detect (before removing the PIVC) because they are located under the medical device and the fixation device.

In addition, the specific nature of paediatrics can make pressure sores difficult to detect. One of the main reasons for this is the difficulty of communicating with children about pain and discomfort.

A pressure ulcer is an ischaemic lesion caused by compression of soft tissue between a hard surface and a bony prominence (7). This prolonged compression causes tissue ischaemia. There are many risk factors for pressure ulcers, which are well described by the EPUAP (European Pressure Ulcer Advisory Panel) and the NPUAP (National Pressure Ulcer Advisory Panel) in their abbreviated reference guide (8).

These include intrinsic factors such as the child's age (level of activity and mobility, skin maturity), nutritional status, peripheral perfusion disorders, certain acute or chronic serious illnesses, and treatments.

Other factors, known as extrinsic or mechanical factors, such as pressure, friction, shear and maceration, are also known to cause pressure ulcers.

In our case, the pressure sores observed at the junction of the catheter and the peripheral venous line extender are mainly related to these extrinsic factors. These are referred to as iatrogenic pressure sores.

Numerous articles mention the fact that children fitted with medical devices are at risk of pressure ulcers. A separate section is devoted to them in the NPUAP's reference guide on the prevention and treatment of pressure ulcers (8).

It also specifies that pressure ulcers associated with medical devices are less studied in children than in adults.

To assess the risk of pressure ulcers in adults, there is a reference assessment scale, the Braden Q scale. This scale is also recommended for children to assess the risk of pressure ulcers related to medical devices. (9)

In a 2017 study, 8% of hospitalised children developed pressure ulcers, 2% of which were related to immobility and 6% to medical devices. (9)

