2.1.1. Primary objective

Compare the incidence of pressure sores during standard fixation versus fixation with a compress at the junction between the catheter and the extension tube in a paediatric population.

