2.2.1. Secondary objective(s)

- Compare the severity of pressure ulcers at the catheter/tube junction.
- Compare the duration of peripheral venous catheter retention between the two groups.
- Compare the rate of nosocomial infections related to peripheral venous catheters between the two groups.

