2.2.2. Secondary evaluation criteria

- The severity of pressure ulcers will be assessed using the NPUAP scale

- The duration of catheter retention will be calculated between the time the catheter is inserted and the time it is removed.

- The presence of a nosocomial infection related to the peripheral venous catheter.

This will be defined by a peripheral venous catheter culture $>10^3$ CFU/ml, if the peripheral venous catheter is sent for culture due to suspected infection and in the absence of antibiotic treatment. In the presence of antibiotic treatment, it will be defined by the presence of pus and/or regression of infectious signs within 48 hours of removal of the peripheral venous catheter.

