5.2.2. Statistical justification of the number of subjects

This is a pilot study. To our knowledge, there are currently no data on the assessment of pressure ulcers at the junction of the catheter with the extension tube or peripheral venous line tubing in paediatric hospitalised patients.

This study will therefore provide reliable data on these pressure ulcers in both standard care (without compresses) and will also provide data on the benefits of compresses for pressure ulcer prevention.

With a total of 346 patients, our study will highlight a difference of at least 15% between the two groups (80% power and 5% alpha risk). **In order to guarantee the power of the study, a total of 360 patients will be randomised.**

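### Section 5.2.1 pre-specifies no between-arm effect with a confidence interval; its only model adjusts for a post-randomisation outcome and leaves out age, which is known at randomisation

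*Combined protocol and SAP*

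**What the plan says.** Section 5.2.1 gives the primary analysis in two steps. First: "The percentage of patients will be presented with a 95% confidence interval in the two groups and will be compared using a Chi-square test". Then: "In a second step, the two groups will be compared using logistic regression to take into account the duration of catheter retention". It names no risk difference, risk ratio or odds ratio, and no interval for a contrast between the arms.

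Other sections call for such a contrast. The primary objective (2.1.1) is to "Compare the incidence of pressure sores during standard fixation versus fixation with a compress". The sample-size section (5.2.2) says that "our study will highlight a difference of at least 15% between the two groups", and that the pilot "will also provide data on the benefits of compresses for pressure ulcer prevention".

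On the covariate in the model, section 2.2.2 states: "The duration of catheter retention will be calculated between the time the catheter is inserted and the time it is removed". Section 2.2.1 makes the same quantity a secondary objective: "Compare the duration of peripheral venous catheter retention between the two groups".

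On age, section 1.1 lists intrinsic risk factors for pressure ulcers that include "age (level of activity and mobility, skin maturity), nutritional status, peripheral perfusion disorders". Section 5.2.8 requires month and year of birth at randomisation and says that randomisation is not stratified. No comparison in section 5.2 uses age.

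**The concern.** The trial's question is how much the compress lowers the risk of an ulcer. The planned output is a p-value and two separate intervals, which do not state that effect or its uncertainty. A pilot meant to inform a larger multicentre study (section 1.1) needs both.

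The second-step model is the only place where an adjusted effect would appear, and it is a poor source for one. Retention begins at insertion, which follows randomisation, so the compress may change it. Conditioning on it can then remove or distort part of the compress effect. Its odds ratio is also on a different scale from the one used for sizing. Because the plan does not call this model exploratory, a reader could take it as the adjusted treatment effect.

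Age has none of these problems. It is fixed before randomisation, is already collected, and spans 1 month to 18 years. It is handled neither in the design nor in the analysis. If the plan stays silent, the effect measure, the covariates and the result that governs can all be chosen after the data are seen.

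**Working it through.** **Inputs.** From the documents: 360 randomised 1:1, so 180 per arm; a 15-point difference; 80% power; alpha 5% (taken as two-sided); a stated requirement of 346. The documents give no event rate, age distribution or age effect, so these are assumptions and are varied.

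**The plan's own figure.** The pooled two-proportion formula per arm is n = [1.96·√(2p̄(1−p̄)) + 0.842·√(p₁(1−p₁)+p₂(1−p₂))]² / (p₁−p₂)². With 55% v 40% it gives 172.8, so 173 per arm and 346 in total, the stated number. With 50% v 35% the total is 340, and with 30% v 15% it is 242. At 55% v 40% with a continuity correction it would be 372, so the stated number matches the uncorrected Chi-square at rates near one half.

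**What a between-arm interval would show.** The Newcombe interval combines the two Wilson intervals (l, u): lower = d − √[(p₁−l₁)² + (u₂−p₂)²], upper = d + √[(u₁−p₁)² + (p₂−l₂)²]. With 99/180 v 72/180 events, the Wilson intervals are 47.7% to 62.1% and 33.1% to 47.3%.

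| Events, no compress v compress | Reduction (points) | Newcombe 95% CI | Odds ratio |
|---|---|---|---|
| 99 v 72 (55% v 40%) | 15.0 | 4.7 to 24.9 | 0.545 |
| 90 v 63 (50% v 35%) | 15.0 | 4.8 to 24.8 | 0.538 |
| 54 v 27 (30% v 15%) | 15.0 | 6.4 to 23.4 | 0.412 |

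In the first row the Chi-square gives z = 2.85, p = 0.004. The Wald interval there is 4.8 to 25.2, so the choice of formula matters little. The same 15 points is an odds ratio of 0.55 or 0.41 depending on the base rate, so an odds ratio alone cannot be read back to the sizing scale.

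**What age adjustment adds.** Simulation of 8,000 trials per scenario, with ages uniform from 0 to 18 years. The uncorrected Chi-square is compared with a risk difference standardised from a logistic model on arm and age (delta-method standard error). At 55% v 40%:

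| Age odds ratio across the range | Half-width, adjusted (points) | Power, Chi-square / adjusted | The two disagree |
|---|---|---|---|
| 1 | 10.17 | 82.4 / 82.4% | 0.7% |
| 2 | 10.12 | 81.0 / 81.3% | 2.0% |
| 3 | 10.05 | 81.6 / 82.8% | 3.3% |
| 6 | 9.86 | 82.0 / 84.2% | 5.5% |

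In patients, the gain is (10.17/10.05)² = 1.02, about 2%, at 3-fold and (10.17/9.86)² = 1.06, about 6%, at 6-fold. At 30% v 15% the half-width goes from 8.46 to 8.27 points between 1-fold and 6-fold. Across all scenarios the adjusted interval covered in 94.4% to 95.4% of trials, and its type I error was 4.8% to 5.5% (Chi-square 4.6% to 5.4%).

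The linear age term also held up when it was the wrong shape. With half the patients under 2 years and either a 3-fold step at that age or a U-shaped effect, coverage was 95.0% and the mean estimate stayed between 14.9 and 15.0 points.

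**What conditioning on duration can do.** This is an illustration with assumed effects. Suppose the compress has no direct effect, lengthens retention by 0.5 SD, and retention raises the log-odds of an ulcer by 0.5 per SD. The duration-adjusted odds ratio is then about 1.00 and is significant in 5% of trials, while the unadjusted model detects the total effect in 19%. With an unmeasured cause shared by retention and ulcers, the adjusted odds ratio moves to about 0.88 although there is no direct effect. If the compress does not change retention, it stays near 1.

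**Missing outcomes.** Section 5.2.5 counts them as no ulcer. With 5% missing in both arms, 15.0 points becomes 0.95 × 15.0 = 14.25, for either estimate.

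**The case against.** Nothing planned is invalid. The Chi-square is sound, and anyone with the two percentages can work out the unadjusted difference and its interval. The gain from age is slight unless age is strongly prognostic; the documents give no age effect, and section 1.1 attributes these lesions mainly to extrinsic factors. If the Chi-square keeps the alpha, adjustment adds no power, and an adjusted estimate beside an unadjusted test will sometimes disagree with it. The duration model already comes second, and duration is a sensible measure of exposure to the pressure source. No passage says the compress changes it. Other baseline variables may be collected, since the data list in Appendix 3 is given by title only. An amendment may also be needed.

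Most of this stands, and it limits the size of the point. This is an improvement to the plan and does not correct an invalid test. The precision gain may be close to nil, and the power figures would count only if alpha were moved to the adjusted estimate.

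It does not remove the point. That a reader can derive a difference does not mean the plan has fixed the scale, the covariate and the result that governs. The concern about duration needs no proof that the compress alters it, because the trial itself sets out to compare it between arms. A rule in the text settles any disagreement between test and interval. The plan should also say that the Chi-square is uncorrected: at 55% v 40% with 180 per arm, simulated power is 81.9% without the correction and 78.9% with it.

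**Conclusion.** The concern holds. Section 5.2.1 pre-specifies no between-arm effect with an interval, its only model conditions on a post-randomisation outcome, and age enters no comparison. The main loss is in what the trial will report: a result with p = 0.004 can go with a reduction anywhere from 4.7 to 24.9 points, and the plan does not commit to showing that range. The added precision from age is secondary: about 2% more patients' worth at a 3-fold age effect, 6% at 6-fold, and no loss of power if age is irrelevant. The intervals rest on assumed event rates, and the age figures also on assumed ages and age effects. The reading of the plan rests on its text alone. The change should be made, but the trial's primary test does not depend on it.

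**What to change.** Add to section 5.2.1, for the ITT population:

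1. The effect estimate is the risk difference (compress minus no compress) with its 95% CI, from a logistic regression on arm and age (one linear term, in years), standardised over all randomised patients, with a delta-method interval.
2. The unadjusted risk difference with a Newcombe 95% CI is shown beside it.
3. The Chi-square without continuity correction alone governs the 5% alpha, also when the adjusted interval disagrees with it.
4. The duration-adjusted logistic regression is exploratory.
5. Both risk differences use the missing-data rule of section 5.2.5.

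The cost is a few sentences and slightly more analysis, possibly through the amendment route in section 7.8. The sample size and the data collected stay the same, and the test changes only in that its uncorrected form is named. The text should be settled before the data are analysed.
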